	Absolute values and change from baseline in ravulizumab concentrations over time
To characterize the potential for immunogenicity of ravulizumab in adult participants with LN or IgAN	Incidence of ADAs over time
Safety (Both Cohorts)	
To characterize the safety and tolerability of ravulizumab in adult participants with LN or IgAN	Incidence of AEs and SAEs over time

Abbreviations: ADA = antidrug antibody; AE = adverse event; C3, C4, and C5 = complement components 3,4, and 5; CRR = complete renal response; eGFR = estimated glomerular filtration rate; IgAN = immunoglobulin A nephropathy; LN = lupus nephritis; PD = pharmacodynamics; PK = pharmacokinetics; PRR = partial renal response; SAE = serious adverse event; SLE = systemic lupus erythematosus; UPCR = urine protein to creatinine ratio

Overall Design

Study ALXN1210-NEPH-202 is a Phase 2, randomized, double-blind, placebo-controlled, multicenter study of ravulizumab in addition to allowed concomitant therapy consistent with the standard of care in 120 adult participants (18 to 75 years of age) with either LN or IgAN. All participants must be naive to complement inhibitor treatment and have either a diagnosis of LN with an active flare or IgAN based on kidney biopsy, estimated glomerular filtration rate (eGFR) \geq 30 mL/min/1.73m², and proteinuria [defined as urine protein to creatinine ratio (UPCR) \geq 1 g/g from one 24-hr urine collection (LN cohort) or as mean protein \geq 1 g/24-hr from 2 valid 24-hr collections (IgAN cohort)]. Participants in the IgAN cohort must have been treated with stable doses of the maximum tolerated renin-angiotensin system (RAS)-inhibiting medications and have controlled, stable blood pressure (< 140/90 mmHg) for \geq 3 months prior to Screening.

Approximately 60 participants in each disease cohort will be randomly assigned in a 2:1 ratio to receive ravulizumab or placebo (40 ravulizumab, 20 placebo). Randomization will be stratified by whether corticosteroid induction treatment was initiated prior to Screening versus during the Screening Period for participants in the LN cohort and by mean proteinuria (1 to 2 g/day versus $>$ 2 g/day) from 2 valid 24-hr urine collections during Screening Period for participants in the IgAN cohort.

The study consists of an up to 6-week Screening Period, a 26-week Initial Evaluation Period, a 24-week Extension Period, and a 36-week post-treatment Follow-up Period.

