During the Initial Evaluation Period, all participants will receive a weight-based loading dose of ravulizumab or placebo on Day 1, followed by maintenance doses of ravulizumab or placebo on Day 15 and then once every 8 weeks (q8w) thereafter. Loading and maintenance doses will be determined based on body weight (see table below). All participants will receive allowed

concomitant therapy consistent with the standard of care for participants with LN and IgAN throughout the study.

During the 24-week Extension Period, participants in the LN cohort will continue to receive their randomized allocation of study drug (ravulizumab or placebo) q8w. Participants in the LN cohort will receive additional standard of care therapy in the event of a protocol-defined Renal Flare or Severe Extrarenal systemic lupus erythematosus (SLE) Flare. Approved novel treatment(s) for LN is allowed. Additional standard of care therapy for participants with Suboptimal Response is allowed at the clinical discretion of the Investigator in conversation with the Medical Monitor. For the IgAN cohort, participants in the placebo group will receive a blinded loading dose of ravulizumab at Week 26 and participants in the ravulizumab group will receive a blinded ravulizumab dose of 900 mg at Week 26. Starting Week 28, all participants in the IgAN cohort will receive open-label weight-based doses of ravulizumab q8w until the end of the Extension Period.

During the 36-week Post-treatment Follow-up Period, all participants will continue to receive standard of care and will be monitored for safety, clinical events of interest, and kidney function. Participants who discontinue study drug early and agree to remain in the study should continue to attend their scheduled protocol visits until Week 50. During these visits, all assessments except for study drug administration should be performed according to the Schedule of Assessments. Participants who withdraw from the study will be followed for safety until 8 weeks after the last dose of study drug. The end of study is defined as the last participant's last visit in the Post-treatment Follow-up Period.

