Days and Window	D183	D197 ± 7	D253 ± 7	D309 ± 7	D351 ± 7	
Participant safety card review		X	X	X	X	
Pharmacokinetic and Pharmacodynamic Assessments						
Blood samples for PK/PD		T/P	T/P	T/P	X	Collect samples at any time during the Week 50/ED Visit
Blood samples for ADA		T	T	T	X	Collect samples at any time during the Week 50/ED Visit
Exploratory Assessments						
SF-36					X	
EQ-5D-5L					X	
Blood and urine samples for biomarkers		X	X	X	X	
Kidney biopsy (if indicated per Investigator) ^e	Continuous monitoring				Send the site pathology report and microscopy slides to the Central Pathology Laboratory (Section 8.1.5.3)	
Administration of Study Intervention						
Allowed concomitant IgAN therapy	Continuous monitoring				Section 6.5.2	
Ravulizumab ^f	X	X	X	X		Administer after all other required tests/procedures

Note: During the Extension Period, the IgAN placebo group will switch to ravulizumab such that all IgAN participants will be treated with ravulizumab when the study becomes open label for the IgAN group. Participants in the ravulizumab group will receive a blinded ravulizumab dose of 900 mg at Week 26 and continue to receive the weight-based dosing thereafter.

^a For participants who discontinue the study prior to the end of the Extension Period, the ED Visit should be completed as soon as possible. In addition, a Follow-up Phone Call will be performed 8 weeks following the participant's last dose of study drug to collect concomitant medications, nonpharmacological therapies and procedures, and AEs.

^b Weight should be obtained at every visit and measured predose on dosing visits. The dose regimen is based on the last recorded study visit body weight. If the study drug is prepared the night before a visit, the weight from the most recent study visit should be used.

^c Vital sign measurements include systolic and diastolic BP, pulse oximetry, heart rate, respiratory rate, and temperature. On dosing days, vital signs will be taken predose.

^d Single 12-lead ECG will be collected at any time on Day 351 and the ED Visit. Participants must be supine for approximately 5 to 10 minutes before ECG collection and remain supine but awake during ECG collection.

Table 4: Schedule of Activities During the Extension Period: Week 26 Dose Administration, Week 28 to Week 50 Visits (IgAN Cohort)

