5.7.2. Immunogenicity Analyses

All immunogenicity analyses will be performed on the Safety Set.

The incidence of ADAs to ravulizumab will be summarized descriptively separately for each disease cohort by treatment group at baseline and each postbaseline time point. Immunogenicity variables include ADA status categories, ADA response categories, ADA, or neutralizing antibody (NAb) incidence and titer over the duration of the study as follows:

ADA status categories:

- **ADA negative:** An ADA-negative signal in the ADA assay at all timepoints collected for ADA analysis
- **ADA positive:** An ADA-positive signal in the ADA assay at any timepoint collected for ADA analysis

Participants who are ADA positive may be further categorized into ADA response categories as follows:

- **Pre-existing immunoreactivity:** An ADA-positive response with either of the following 2 conditions met:
 - ADA-positive response at baseline with all post-first-dose ADA results negative
OR
 - ADA-positive response at baseline with all post-first-dose ADA responses less than 4-fold over the baseline titer level
- **Treatment-emergent ADA responses:** An ADA-positive response post-first-dose when baseline results are negative or missing
- **Treatment-boosted ADA responses:** An ADA-positive response post-first-dose that is \geq 4-fold over the baseline titer level when the baseline result is positive

Treatment-emergent or treatment-boosted ADA responses may be further categorized as follows:

- **Persistent:** ADA responses with 2 or more consecutive ADA-positive samples separated by at least a 16-week period, with no ADA-negative samples in between, irrespective of missing samples
- **Indeterminate:** ADA-positive sample only at the last collected sample
- **Transient:** ADA response that is neither a persistent nor an indeterminate response

ADA-positive samples will be further characterized for neutralizing activity in the NAb assay. NAb status categories are as follows:

- NAb positive
- NAb negative

Associations between ADA response categories and serious and severe adverse events may be explored, including SAEs like systemic hypersensitivity, anaphylaxis, injection/infusion site reactions lasting more than 24 hours, and other immune related SAEs.

Associations between ADA response categories and key efficacy endpoints or variables may be explored to assess the potential impact of immunogenicity on drug efficacy.

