6.1.2. Definition of Baseline Values

For the Initial Evaluation Period, baseline is defined as the last available assessment value prior to the first dose of study intervention. For the Extension Period, baseline is defined as the last available assessment prior to the first dose of study intervention administered in the Extension Period.

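### SAP 5.7.2 labels an ADA response Transient even when its last two or more samples are still positive, if that run spans under 16 weeks

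*SAP*

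**What the plan says.** SAP 5.7.2 (Immunogenicity Analyses) introduces the split as optional: "Treatment-emergent or treatment-boosted ADA responses may be further categorized as follows". The three classes are:

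- Persistent: "2 or more consecutive ADA-positive samples separated by at least a 16-week period, with no ADA-negative samples in between", with missing samples disregarded.
- Indeterminate: "ADA-positive sample only at the last collected sample".
- Transient: "ADA response that is neither a persistent nor an indeterminate response".

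The same section summarizes ADA incidence at baseline and at each later time point by treatment group, and lists every ADA sample with its titer by participant. It adds that associations of ADA response categories with serious and severe adverse events, and with key efficacy endpoints, may be explored.

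The sampling days are in Protocol 1.3, in the rows headed "Blood samples for ADA". After the Day 1 baseline, LN samples fall at Weeks 4, 10, 26, 34, 42 and 50 (Tables 1 and 3). IgAN samples fall at Weeks 4, 10, 26, 28, 36, 44 and 50 (Tables 2 and 4). Table 5, covering post-treatment follow-up, has no ADA row.

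In the IgAN cohort, "participants in the placebo group will receive a blinded loading dose of ravulizumab at Week 26" (Protocol 1.1). For the Extension Period, "baseline is defined as the last available assessment prior to the first dose of study intervention administered in the Extension Period" (SAP 6.1.2). For this switch arm, baseline is therefore the Week 26 predose sample, and the informative ADA samples are those at Weeks 28, 36, 44 and 50.

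**The concern.** A reader of a table column headed Transient will expect antibody that appeared and then went away. The rule does not secure that, because it never asks whether a negative sample followed.

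The ordering is also illogical. One positive at the last sample leaves the course unknown, and the label says so. A second positive immediately before it makes continuing ADA more likely, yet the label moves to Transient.

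The schedule makes this reachable. ADA sampling stops at Week 50, and the switch arm has only 24 weeks between first exposure and the last scheduled sample, so a response first detected in the later part of that interval cannot build up 16 weeks. What is at stake is the meaning of one descriptive column, which would mix responses that ended with responses still present when sampling stopped.

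**Working it through.** The plan gives no figure to reproduce, so the check applies the three definitions to the scheduled days.

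**Inputs.** Threshold: 16 weeks = 112 days. IgAN Extension samples: Days 197, 253, 309 and 351, each ± 7 (Protocol Table 4). LN samples: Days 29, 71, 183, 239, 295 and 351 (Tables 1 and 3; ± 7 for the last three). First switch-arm exposure: Day 183. I read the 16-week separation as running from the first to the last positive of an unbroken run.

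**Formula.** Span in weeks = (351 − onset day) / 7, for positivity sustained from onset through Week 50.

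| Cohort, first positive | Span | Positives | Label now |
|---|---|---|---|
| IgAN, Week 28 | (351 − 197)/7 = 22 | 4 | Persistent |
| IgAN, Week 36 | (351 − 253)/7 = 14 | 3 | Transient |
| IgAN, Week 44 | (351 − 309)/7 = 6 | 2 | Transient |
| IgAN, Week 50 | 0 | 1 | Indeterminate |
| LN, Week 34 | (351 − 239)/7 = 16 | 3 | Persistent, exactly at the threshold |
| LN, Week 42 | (351 − 295)/7 = 8 | 2 | Transient |
| LN, Week 50 | 0 | 1 | Indeterminate |

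Onset at Weeks 4, 10 or 26 is Persistent in both cohorts (46, 40 and 24 weeks). The IgAN Week 36 and Week 44 rows apply to the arm on ravulizumab throughout as well as to the switch arm.

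**Visit windows.** Week 36 to Week 50 spans 12 to 16 weeks and reaches 16 in 1 of the 15 × 15 = 225 day combinations. Week 44 to Week 50 spans 4 to 8 weeks and never reaches it. LN Week 34 to Week 50 is nominally 112 days but ranges from (344 − 246)/7 = 14 to (358 − 232)/7 = 18 weeks, so actual dates decide the label.

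**Early leavers.** A participant positive at Weeks 4 and 10, whose Week 10 sample is the last collected, has a run of (71 − 29)/7 = 6 weeks and is Transient while still positive.

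**All switch-arm patterns.** Four samples give 16 positive/negative patterns: 1 all negative, 2 Persistent, 1 Indeterminate, 12 Transient. Of the 8 that are positive at Week 50, 6 are Transient, 1 Persistent and 1 Indeterminate. Of those 6, 3 are intermittent with a lone positive at Week 50, and 3 end with two or more positives.

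**Share of responders.** The documents give no onset distribution. If onset were uniform over Days 183 to 351 (168 days) and positivity sustained, the split would be Persistent 14/168 = 8.3%, Transient 112/168 = 66.7% and Indeterminate 42/168 = 25.0%. Under other distributions the Transient share could be anything from 0% to 100%.

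**Expected counts.** The planned allocation is "40 ravulizumab, 20 placebo" per cohort (Protocol 1.1). Protocol 2.3.1 (Table 6) reports fewer than 1% ADA-positive in earlier Phase 2 and 3 studies. Taking 1%, the 20 switch-arm participants give 20 × 0.01 = 0.2 expected positives and a 1 − 0.99^20 = 18% chance of at least one.

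**The case against.** Several stronger readings are tempting, and the documents do not support them.

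- A reader might infer that nearly all late seroconversion in the switch arm gets the wrong label. Onset at Week 28 is Persistent and onset at Week 50 is properly Indeterminate, so 2 of 4 onset visits are affected. The share of participants is unknown.
- A reader might infer that these responses are reported as resolved. The SAP never gives Transient that meaning, and by-visit incidence and the sample listings would show the positive Week 50 result.
- A reader might infer that the planned comparison of ADA with safety and efficacy is biased. That comparison is only something that may be explored. It refers to ADA response categories, which in the layout of SAP 5.7.2 are most naturally the parent classes (pre-existing, treatment-emergent, treatment-boosted). Relabelling within the sub-split would leave those unchanged.
- A reader might infer that persistence is understated. A corrected rule moves the affected responses to Indeterminate. The Persistent count changes only where visit dates straddle the 16-week threshold.

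The split is also optional, carries no hypothesis test or dosing decision, and will probably apply to very few people. All of this stands and limits the importance of the point. It does not remove the gap: the listings let a reader find a wrong label, but they do not correct the category table.

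**Conclusion.** The gap is real and minor. As written, a non-persistent response that is positive at its last two or more samples over less than 16 weeks is called Transient. For sustained positivity on scheduled days this means onset at Week 36 or 44 in IgAN and at Week 42 in LN, plus early leavers with a short terminal run. A participant with an earlier qualifying 16-week run is Persistent whatever follows, and is not affected.

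The result rests on the first-to-last reading of the 16-week separation. If adjacent samples must themselves be 16 weeks apart, switch-arm onset at Week 28 also becomes Transient (3 of 4 visits), while Week 50 onset stays Indeterminate. The expected count assumes that the earlier ADA rate carries over to these populations. No efficacy conclusion depends on the point, but with so few positives a single label can change the reported split.

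**What to change.** Replace the three definitions in SAP 5.7.2 with a hierarchy applied in order:

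1. Persistent: as now defined, stated as first to last positive of an unbroken run, with the 16-week rule measured in nominal visit weeks.
2. Indeterminate: not Persistent, and the last collected sample is ADA-positive.
3. Transient: not Persistent, and the last collected sample is ADA-negative.

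The classes are then mutually exclusive and cover every response. Sustained switch-arm onset at Weeks 28, 36, 44 and 50 becomes Persistent, Indeterminate, Indeterminate and Indeterminate. Across the 15 patterns with any positive, the split goes from 2 Persistent, 1 Indeterminate and 12 Transient to 2, 7 and 6. A looser patch, asking only that some negative sample follows a positive one, would not do: an intermittent pattern ending positive at Week 50 could then meet both Indeterminate and Transient.

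Nominal weeks settle the cases that sit exactly on the threshold, such as LN Week 34 to Week 50 and IgAN Week 28 to Week 44 (309 − 197 = 112 days). Samples taken at an early-discontinuation visit need a stated week; the analysis-visit assignment in SAP 6.1.5 could supply it.

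The cost is a few sentences in the SAP and a small programming change. No new samples or data are needed.

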5.7.3. COVID-Related Analyses

The following COVID-19 related data will be collected in this study:

- Modified and missed study visits (and COVID-19 related reasons)
- Discontinuations impacted by COVID-19
- COVID-19 exposure
- Missed infusions due to COVID-19

- AEs related to COVID-19
- Protocol deviations related to COVID-19

A listing of all participants affected by these COVID-19 related study disruptions will be provided by participant identifier and investigative site, including a description of the COVID-19 related study disruption.

The number of participants with missed study visits and the reasons for missed study visits (COVID-related or other) will be summarized by treatment groups and overall.

In addition, the number of participants with modified study visits and the reasons for modified study visits (COVID related or other) will be summarized by treatment group and overall. Similarly, the number of participants with modified study visits and the ascertainment method for the modified visit will be summarized by treatment group and overall. A by-participant listing of visit status and assessment ascertainment for participants with modified visits will also be produced.

To assess the impact of change in endpoint ascertainment, descriptive statistics of the primary and key secondary endpoints by method of assessment (in clinic versus alternative method) will be provided using the FAS.

The number of participants with known exposure to COVID-19 will be summarized for pretreatment known exposure and treatment-emergent known exposure by treatment group and overall. A by-participant listing of participants with COVID-19 known exposure or diagnosis will also be produced.

Missed infusions due to COVID-19 will be summarized with overall study intervention exposure as specified in Section [5.6.1](#).

An overall summary table of TEAEs related to COVID-19 will be presented. In addition, the number of TEAEs related to COVID-19 and the number and percentage of participants with TEAEs related to COVID-19 will be presented by SOC and PT.

Protocol deviations related to COVID-19 will be summarized with the overall protocol deviations as specified in Section [6.2.4](#).

5.7.4. Subgroup Analyses

Summaries of the primary efficacy endpoint will be presented by the following subgroups for both cohorts:

- Age at Screening (18 to 65 years, > 65 years)
- Gender (female, male)
- Baseline eGFR (30 to 60, > 60 to 90, > 90 mL/min/1.73 m²)
- Baseline C3 (\leq first quartile, > first quartile)
- Baseline C4 (\leq first quartile, > first quartile)

For the LN cohort, summaries of the primary efficacy endpoint will be presented by the following additional subgroups:

- Duration of LN disease (\leq median, $>$ median)
- Duration of SLE disease (\leq median, $>$ median)
- Race/ethnicity (African American, non-African American)
- Baseline proteinuria (\leq 3.5 g/g, $>$ 3.5 g/g)
- Corticosteroid induction timing (prior to Screening, during Screening Period)
- LN class based on local pathology (III, III/V, IV, IV/V)
- LN class based on central pathology (III or III/V, IV or IV/V)
- TMA on renal biopsy based on central pathology (yes, no)
- Disease status (naïve, relapse)
- Baseline renal biopsy activity index based on central pathology (\leq median, $>$ median)
- Baseline renal biopsy chronicity index based on central pathology (\leq median, $>$ median)
- Immunosuppressants: Hydroxychloroquine use (yes, no)
- ACE inhibitors and ARBs use (yes, no)
- Hypertension history (yes, no)
- Blood pressure: systolic, diastolic (\leq median, $>$ median)
- Background medication dose on Day 1: MMF (\leq 1500mg/day, $>$ 1500mg/day)
- Background medication dose on Day 1: Prednisone (\leq median, $>$ median)
- Baseline serum creatinine (\leq 100umol/L, $>$ 100umol/L)

For the IgAN cohort, summaries of the primary efficacy endpoint will be presented by the following additional subgroups:

- Duration of disease (\leq 1 year, 1 to 5 years, $>$ 5 years)
- Race (Asian or Other Pacific Islander, non-Asian or Other Pacific Islander)
- Baseline proteinuria (1 to 2 g/day, $>$ 2 g/day)
- Baseline MEST-C score based on central pathology (M0, M1, E0, E1, S0, S1, T0, T1, T2, C0, C1, C2)
- Baseline C3 staining based on central pathology (presence, absence)
- Baseline C4d staining based on central pathology (presence, absence)
- SGLT2 use (yes, no)

For the IgAN cohort, summaries of the primary efficacy endpoint by subgroups of baseline MEST-C score, baseline C3 staining, and baseline C4d staining will be presented separately for

participants with biopsies within 1 year of randomization and for participants with biopsies greater than 1 year before randomization, if feasible, based on sample size.

Given that the number of participants in some subgroups may be limited, subgroup categories may be combined as appropriate. Otherwise the subgroup analysis may not be performed if deemed infeasible based on sample size.

Forest plots will be produced showing the results of the primary efficacy endpoint (percentage change in proteinuria from baseline to Week 26) with means and corresponding CIs for each subgroup described above.

5.8. Interim Analyses

5.8.1. Dose Confirmation Analysis

To ensure the adequacy of the dose regimen, an interim PK/PD analysis for dose confirmation will be conducted by an independent clinical pharmacologist. The interim PK confirmation analysis will be conducted using masked PK/PD data from the first 10 participants treated with ravulizumab (a minimum of 3 participants in each disease-specific cohort), using data cut when the tenth participant reaches 2 weeks post-first-dose (ie, at Day 15). The PK dataset for review will include:

- Day 1 maximum concentration (C_{max}), Day 15 trough concentration (C_{trough}), and C_{max} for all 10 participants.
- PK data beyond Day 15 C_{max} timepoint (eg, Day 29 PK) may be included in the dataset (availability depending upon the enrollment rate).
- Total and free C_5 data associated with above timepoints and ADA data will be included in the dataset as supportive evidence.

If observed Day 1 C_{max} , Day 15 C_{max} and C_{trough} values, and other available PK/PD data are within the expected range, the study will proceed unchanged. If the totality of the available PK/PD data are not within the expected range, a dose regimen adjustment may be necessary for all participants or for a subset of participants. If all participants require a dose regimen adjustment, enrollment will be paused until a new regimen is determined. If dose regimen adjustment is only required for a subset of participants, enrollment may continue in the subset not requiring dose adjustment. In the event of dose adjustments, the participants treated with the previous dose will switch over to the new dose and continue treatment on study but will be excluded from the primary efficacy analysis. Replacement participants may be enrolled to preserve study power.

